#### 11.2.2.2 Secondary “Effectiveness” Endpoints Analyses

Secondary effectiveness endpoints include surgeon and patient closure method satisfaction, scar appearance satisfaction and patient pain and comfort surveys. All results will be summarized by treatment.

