| Secondary Effectiveness Endpoints | 
 
• Surgeon evaluation including: 
 
○ Closure Method Satisfaction
 
○ Scar Satisfaction
 
○ Wound Healing as judged by the surgeon using the WES (Wound Evaluation Scale) at the 6 to 8 week final post op visit.
 
 
 
• Physical Therapist 
 
○ Range of Motion (ROM) Measurements
 
 
 
• Patient experience including: 
 
○ Pain (General Post-Operative & Incisional)
 
○ Closure Method Comfort
 
○ Closure Method Satisfaction
 
○ Scar Satisfaction
 
 
 
 |
| Primary Safety Endpoint           | The incidence and severity of adverse effects associated with Zip device and standard steel staple usage.  |
| Secondary Safety Endpoint         | None   |
| Follow-Up Schedule                | The study will be considered complete (with regard to the primary endpoint) after 22 subjects have completed the 6 to 8 - week follow up visit.  |
| Inclusion Criteria                | 
 
1. Patients 18 years of age and older;
 
2. Patients requiring epidermal closure after bi lateral total or partial (unicompartmental) knee arthroplasty;
 
3. Patients willing to be evaluated at discharge, 2 weeks, and at the 6 to 8 week post op.
 
  |
| Exclusion Criteria                | 
 
1. Known bleeding disorder not caused by medication
 
2. Known personal or family history of keloid formation or scar hypertrophy
 
3. Known allergy or hypersensitivity to non-latex skin adhesives
 
4. Atrophic skin deemed clinically prone to blistering
 
5. Any skin disorder affecting wound healing
 
6. Any other condition that in the opinion of the investigator would make a particular patient unsuitable for this study
 
   |

| Study Administration           |   |                     |
|--------------------------------|---|---------------------|
| Manager
Clinical
Affairs | [name]
[name],
[name]
[contact] | [contact] (cell) |

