#### 3.2 **Summary of Findings from Previous Studies**

##### 3.2.1 Pre-clinical Studies

Preclinical feasibility testing of the ZipLine technology using a chronic porcine model was conducted in 2010. Surgical incisions were closed either with the ZipLine technology, or absorbable subcuticular sutures. Devices were removed at two weeks post-operatively, and resulting scars were evaluated at 6-weeks by a blinded panel of four board-certified plastic surgeons. Results revealed excellent cosmesis when compared to subcuticular suture controls.

Below is an example of comparative outcomes at 2 weeks post-op:

ZipLine Closure

Subcuticular Suture Closure

The Cosmetic Visual Analog Scale (CVAS) and ordinal Wound Evaluation Scale (WES) were used to evaluate photographs of each scar from the test subjects. Evaluators were blinded to the type of closure method used for each wound.

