## 5 Study Objective

[figure not shown]
The primary objective of this post-market study is to evaluate scar appearance / cosmesis associated with the use of the Zip Surgical Skin Closure versus conventional staples when utilized for surgical wound closure after bilateral knee arthroplasty (unicompartmental or total). For safety analysis, the rate of adverse events up to 8 weeks post-surgery will be compared between the ZipLine Surgical Skin Closure and standard staples.

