**Table 1. Study Event Schedule**

|  | Before Procedure | Uni/TKA Procedure-Zip device or staple control Placement | Discharge 0-3 days Post Procedure | 14 days (+/-1 week) post Procedure | 6-8 weeks** (+/-4 days) post Procedure |
|--|------------------|--|-----------------------------------|------------------------------------|--|
| Study Initiation:  | X                |  |                                   |                                    |  |
| Informed Consent   | X                |  |                                   |                                    |  |
| Demographics/ Medical History  | X                |  |                                   |                                    |  |
| Clinical Status evaluation/site evaluation prior to wound closure device placement | X                |  |                                   |                                    |  |
| Inclusion / Exclusion Criteria Assessment  | X                |  |                                   |                                    |  |
| Left/Right Knee Randomization to Zip device or staples                             | X                |  |                                   |                                    |  |

|   |   |   |    |   |   |
|---|---|---|----|---|---|
| Photographs Taken   |   |   | X* | X | X |
| Adverse Events/Complications  |   | X | X  | X | X |
| Physician Evaluations (Satisfaction)  |   |   | X  |   | X |
| Physical Therapist Evaluations (ROM)  | X |   |    | X | X |
| Patient Evaluations(Pain, Comfort, Satisfaction)  | X |   | X  | X | X |
| Cosmetic outcome (CVAS, WES)  |   |   |    | X | X |
| Study Exit Form -CRF  |   |   |    |   | X |
| *Optional   |   |   |    |   |   |
| **Final visit will take place between week 6 and week 8 post surgery depending on surgeons standard visit schedule. |   |   |    |   |   |

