## **9.2 Statistical Analysis Plan**

### **9.2.1 General Summary**

CVAS summary statistical results will include, averages standard deviation, range, and Coefficient of Variation (CVs) will be reported for both the control and treatment. Results will include significance testing (t test) with calculated p value(s). Graphic representation of data with distribution analysis of CVAS results will also be presented and summarize. All variables of interest including subject demographics, baseline characteristics, effectiveness and safety endpoints will be summarized.

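### Low-priority, cheap improvement: the secondary endpoints of a within-patient trial are only to be summarised by treatment, with no within-patient estimate and no baseline-adjusted analysis of ROM

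*Combined protocol and SAP*

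**What the plan says.** Section 5.1 makes each subject their own control, with one closure on each knee. Section 9.3 argues that a paired test is more powerful and better suited to this design, but makes the argument for CVAS. The CVAS part of Section 9.2.2 likewise specifies its one-sided paired t test for CVAS alone.

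For the secondary endpoints, Section 11.2.2.2 lists satisfaction, scar appearance, pain and comfort, and stops at "scar appearance satisfaction and patient pain and comfort surveys. All results will be summarized by treatment". Section 9.2.1 adds a general sentence: "All variables of interest including subject demographics, baseline characteristics, effectiveness and safety endpoints will be summarized". The t test in Section 9.2.1 stands among the sentences on CVAS and is not extended to other endpoints.

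Two secondary endpoints in the Synopsis are not named in Section 11.2.2.2: "Range of Motion (ROM) Measurements" and "Wound Healing as judged by the surgeon using the WES (Wound Evaluation Scale" at the final visit. Table 1 schedules "Physical Therapist Evaluations (ROM" before the procedure, at 14 days and at 6 to 8 weeks, and Section 8.4.1 also collects ROM pre-operatively. Section 8.4.6 further records, at the final visit, a scar assessment VAS running from 0 to 10, listed under subject and surgeon ratings. Section 11.2.2.2 does not mention this scale either.

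**The concern.** In a trial where each patient supplies both treatments, the informative quantity is the difference between that patient's two knees. A table of means, or of response counts, for Zip beside one for staples gives the point difference but not its precision, because precision depends on how the two knees agree within patients. Patients' direct preferences are lost in the same way: the tables do not show how many did better with Zip, the same, or worse.

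Section 3.3.2 says the study is meant to measure some or all of the claimed benefits, and greater patient satisfaction is among them. Without a prespecified paired summary, a reader of the report either has no measure of uncertainty for these items or has to improvise one. For ROM, a pre-operative value that could sharpen the comparison is collected, but no planned analysis adjusts for it.

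**Working it through.** **The plan's own figure.** The secondary endpoints have none. The only stated figure is the minimum of 22 pairs for CVAS (Section 9.3: difference 1.0, SD about 1.5, power 90%, alpha 0.025). The normal approximation gives (1.5 × (1.960 + 1.282) / 1.0)² = 23.6, so 24, which is within two of the stated 22; an exact paired t calculation gives 26. That is a separate matter. Here 22 is used only as the number of pairs.

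**Assumed inputs.** The documents give no response rates, SDs or correlations for any secondary endpoint. All values below other than n = 22 are assumptions, shown over a range.

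**Step 1: a yes/no item such as satisfied or not.** Suppose 18/22 are satisfied with Zip and 13/22 with staples. The difference is 5/22 = 22.7 points. The same two margins arise from quite different patient-level results (95% CI by Tango's score method for paired proportions):

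| Both | Zip only | Staples only | Neither | 95% CI, points |
|---|---|---|---|---|
| 13 | 5 | 0 | 4 | +4.5 to +43.4 |
| 11 | 7 | 2 | 2 | -4.5 to +47.0 |
| 9 | 9 | 4 | 0 | -9.7 to +50.3 |

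The by-treatment tables are identical in all three rows. The first interval excludes zero and the other two do not.

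**Step 2: a continuous item.** With equal SDs on the two knees and between-knee correlation rho, the half-width of the paired 95% CI is t(21) × SD × sqrt(2(1 - rho)/22), with t(21) = 2.080:

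- rho 0: 0.627 SD
- rho 0.3: 0.525 SD
- rho 0.5: 0.443 SD
- rho 0.7: 0.343 SD

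Means and SDs by treatment do not show which of these applies. If a reader treated the two columns as independent groups, the half-width would be 2.018 × SD × sqrt(2/22) = 0.608 SD whatever the value of rho. That is 3% narrower than the paired interval at rho 0, and 16%, 37% or 77% wider at rho 0.3, 0.5 or 0.7. The plan does not propose such an interval; the comparison only shows what the tables leave open.

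**Step 3: ROM with baseline adjustment.** Let r be the correlation between the pre-operative and follow-up between-knee differences. Regressing the second on the first multiplies the variance of the estimated Zip-minus-staple difference by (1 - r²) × (1 + 1/(n - 3)). With n = 22 the last factor is 1 + 1/19 = 1.053:

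- r 0: 1.053 (a 5% loss)
- r 0.3: 0.91 × 1.053 = 0.958
- r 0.5: 0.75 × 1.053 = 0.789
- r 0.7: 0.51 × 1.053 = 0.537

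These correspond to 20.9, 23.0, 27.9 and 41.0 unadjusted pairs. A simulation of 200,000 runs gave variance ratios of 1.053, 0.959, 0.791 and 0.541.

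**The case against.** The strongest reply is that nothing here is an error. There is one primary endpoint, the secondary endpoints carry no hypothesis or alpha, and describing them by treatment is a legitimate choice in a post-market study of 22 to 25 subjects. That stands, and it is why this is only an improvement. A paired difference with a CI is itself descriptive, however, so asking for it does not turn these endpoints into tests.

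The numbers also rest wholly on assumed rates and correlations. That stands too: at rho 0 pairing gains nothing, and at r 0 the ROM adjustment costs a little. Side is randomised within patient (Section 8.4.2), so the unadjusted paired ROM difference is not biased by baseline imbalance. Adjustment is only about precision.

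Four stronger readings are tempting, and the documents do not support them.

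- A reader might infer that WES and ROM have been dropped. The general sentence in Section 9.2.1 covers all effectiveness endpoints, so they are only unnamed in Section 11.2.2.2.
- A reader might call the pre-operative ROM unused. It may be summarised as a baseline characteristic under the same sentence. What is missing is a baseline-adjusted analysis.
- A reader might say that the paired information is lost for good. The patient-level records stay in the CRFs (Section 10), and nothing forbids a paired estimate. The loss lies in the planned reporting.
- A reader might extend the point to safety, because the Synopsis ("The incidence and severity of adverse effects associated with Zip device and standard steel staple usage") and Section 5 ("the rate of adverse events up to 8 weeks post-surgery will be compared between the ZipLine Surgical Skin Closure and standard staples") are worded differently. They can be read together, Section 9.2.3 already plans a separate table of closure-device-related events, and no section says that an event unrelated to either knee would be counted under both closures. Safety is therefore not part of this point.

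**Conclusion.** The point holds as a low-priority improvement. For its secondary endpoints the plan does not use the pairing that it recommends for CVAS, and it plans no baseline-adjusted ROM analysis. At 22 pairs, the planned tables could leave a reader unable to tell a CI of +4 to +43 points from one of -10 to +50, or a half-width of 0.34 SD from one of 0.63 SD. Adjusting ROM could cut the variance by about 4%, 21% or 46% at r 0.3, 0.5 or 0.7, at the risk of a 5% loss if r is 0.

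These sizes depend on the assumed values and on the items being recorded separately for each knee. WES is rated on the wound. For ROM and the patient-rated items, Sections 8.4.1, 8.4.5 and 8.4.6 do not say so, and the CRFs are not in the documents. No planned result is made wrong, and the primary CVAS analysis is untouched.

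**What to change.** In Section 11.2.2.2, name WES, ROM and the 0 to 10 scar assessment VAS. State that each item recorded per knee will be reported as a within-patient Zip-versus-staple difference with a 95% CI, labelled supportive with no multiplicity claim:

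- **ROM, incisional pain and scar assessment VAS:** mean paired difference with a t-based CI.
- **Five-point satisfaction and comfort items, and WES** (Section 3.2.1 calls it ordinal: "ordinal Wound Evaluation Scale (WES) were used to evaluate photographs of each scar from the test subjects"): numbers of patients with Zip better, the same or worse, with a CI for better minus worse, or a signed-rank-based estimate with its CI.
- **General pain:** leave descriptive unless it is rated per knee.
- **Time points:** use those already in Sections 8.4.5 and 8.4.6, with the final visit as the main one for WES, ROM and incisional pain. Patient satisfaction with the closure method has no time point in those sections, so state one.
- **ROM baseline:** if pre-operative ROM is recorded per knee, regress the follow-up between-knee difference on the pre-operative between-knee difference, and give the unadjusted paired difference beside it.

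Before finalising, confirm from the CRFs which items are recorded per knee. The cost is SAP wording and a little more analysis, with no new subjects, visits or assessments.

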#### 9.2.3 Safety

Cumulative adverse events from time of closure to final visit (6 to 8 weeks post op) will be collected, analyzed and summarized by closure treatment. Separate tables will be constructed for (a) all reported adverse events, (b) adverse events reported as closure device related, and/or (d) serious adverse events.

The primary safety analysis will be the overall comparison between Zip and staple adverse events.

#### 9.3 *Sample Size Justification*

Since this is a Bilateral Study, with CVAS scores (Scores: 0 – 10), a paired “t” significant test is the most appropriate test as there is only one variable changing with the patients, i.e., type of closure device. A paired “t” test has more statistical power as well, and is more appropriate since the results will be comparing the treatment and control in a paired fashion.

The targeted minimum sample size of n=22 subjects (paired observations) was determined assuming an average difference ( $\Delta$ ) > 1.0, an hypothesized standard deviation of ~1.5, with the Power of Test set at 90%. Alpha Error for the test of differences = 0.025.

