### 5.1 Sample Size

A total of up to 25 subjects (targeted min. n=22) requiring bilateral knee arthroplasty (unicompartmental or total) will be enrolled. There is anticipated patient fall out (screen failures) post procedure due to surgeon not knowing exactly which procedure is required (total or unicompartmental) until time of surgery. Subjects who are initially enrolled in the study and surgery results in a total knee on one side and a unicompartmental on the other side will be exited from the study and not included in the final analysis. Each subject will serve as their own control since one knee closure will be with staples, and the other knee closure with Zip device. The order of patients will be randomized to receive Zip device on one knee and steel staples on the opposing knee.

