### 8.4.3 Procedure

For consented subjects that meet the eligibility criteria, record the relevant data regarding their procedure. Record the following procedure information:

- Treatment and control sides
- Length of incisions
- Note: Subjects who require a total knee on one side and a unicompartmental on the other side will not be included in the final analysis and should be exited from the study.

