### **9.1.4 Missing Data**

Missing or loss data will not be included in the analysis.

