#### **CVAS**

The hypothesis for cosmesis is that use of the Zip Surgical Skin Closure device will result in CVAS results that are significantly superior to standard staples administered. A 1-sided paired “t” test will be performed to reject the  $H_0$  with >95% confidence. Alpha Error for the 1-sided test = 0.025.

The assumption (hypothesis) for CVAS is:

$H_0$ : Zipline CVAS scores will not be superior to CVAS scores for staples.

$H_A$ : Zipline CVAS scores will be superior to CVAS scores for staples.

Since CVAS scores are measured on a 0 – 10 Likert scale for quality of closure, a distribution analysis will also be performed with summary statistics to show that the incisions closed with the Zip devices result in a cosmetically superior scar as compared to the incisions closed with staples.

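### Section 9.3 claims 90% power for 22 pairs; if the SD of 1.5 is that of the paired differences, its inputs give about 85%

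*Combined protocol and SAP*

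**What the plan says.** Section 9.3 (Sample Size Justification) chooses a paired t test on CVAS scores running from 0 to 10. It states: "The targeted minimum sample size of n=22 subjects (paired observations") was determined from an average difference above 1.0 and "an hypothesized standard deviation of ~1.5, with the Power of Test set at 90%. Alpha Error for the test of differences = 0.025". It does not say whether 1.5 is the SD of the within-patient differences or of the scores on one knee, and it gives no correlation between knees.

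The CVAS part of section 9.2.2 makes the test one-sided. It rejects the null hypothesis "with >95% confidence. Alpha Error for the 1-sided test = 0.025".

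The synopsis and section 5.1 allow up to 25 subjects with a minimum target of 22. The follow-up entry in the synopsis regards the study as complete for the primary endpoint once 22 subjects have attended the 6 to 8 week visit. A subject who has a total replacement on one knee and a unicompartmental replacement on the other "will be exited from the study and not included in the final analysis" (section 5.1; section 8.4.3 says the same). Section 9.1.4 adds: "Missing or loss data will not be included in the analysis".

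**The concern.** A sample size presented as the outcome of a calculation should follow from the inputs printed beside it. Here n, alpha, power, difference, SD and test are all given, so the claim can be checked, and on the natural reading of the SD it fails at the n to which it is attached.

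The trial has one primary endpoint and aims to show superiority. Anyone interpreting a non-significant result will rely on the power statement. If the chance of missing the planned difference is about 15% rather than 10%, a null result is weaker evidence against a benefit than the plan implies. Because the SD is not identified, a reader also cannot tell which calculation was done.

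**Working it through.** **Inputs.** From section 9.3: n = 22 pairs, SD = 1.5, power = 90%, alpha = 0.025, paired t test. The difference is given only as above 1.0, so 1.0 is the planning value. One-sided testing at 0.025 comes from section 9.2.2. First reading: 1.5 is the SD of the paired differences.

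**Formula.** Power = P(T > t(1 − alpha, n − 1)), where T has a noncentral t distribution with n − 1 degrees of freedom and noncentrality (difference / SD) × √n.

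**The plan's own figure, n = 22.** Noncentrality = (1.0 / 1.5) × √22 = 3.127. The critical value with 21 df is 2.080. Power = **84.6%**, against 90% stated.

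**Other numbers of evaluable pairs, same inputs.**

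| Evaluable pairs | Power |
|---|---|
| 22 | 84.6% |
| 23 | 86.3% |
| 24 | 87.8% |
| 25 | 89.2% |
| 26 | 90.4% |

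So 26 is the smallest number of pairs that reaches 90%.

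**Normal approximation.** n = ((1.960 + 1.282) × 1.5 / 1.0)² = 23.6, rounded up to 24. Power at 22 is Φ(3.127 − 1.960) = 87.8%. The more lenient method also falls short.

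**What would give 90% at 22 pairs (exact t, one-sided 0.025).** Either a difference of 1.09 with SD 1.5, or an SD of 1.38 with difference 1.0. An SD of 1.45, which rounds to 1.5, gives 86.9% with difference 1.0.

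**A different alpha.** At one-sided 0.05, 22 pairs give 91.6% and 21 pairs are enough for 90%. The stated n fits that alpha, but nothing in the documents shows it was used, and it contradicts the 0.025 printed in both sections.

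**Second reading: 1.5 is the per-knee SD.** The SD of the differences is then 1.5 × √(2(1 − ρ)), where ρ is the between-knee correlation. The documents give no ρ, so the values below are assumptions.

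| ρ (assumed) | SD of differences | Power at 22 pairs |
|---|---|---|
| 0 | 2.12 | 56% |
| 0.25 | 1.84 | 68% |
| 0.5 | 1.50 | 85% |
| 0.6 | 1.34 | 91.5% |
| 0.75 | 1.06 | 99% |

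Reaching 90% needs an SD of differences of 1.38, so ρ = 1 − 1.38² / (2 × 1.5²) ≈ 0.58.

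**The case against.** The strongest reply is that the SD is unidentified, so 90% is not shown to be wrong: on the per-knee reading a correlation of 0.58 or more would deliver it, and two knees of one patient may well be correlated. That stands as a limit on the conclusion. It does not support the plan's figure, because that reading rests on a correlation the plan never states. Section 9.3 also speaks of paired observations, an average difference and a test of differences, so the SD of differences is the natural reading.

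A second reply is that the inputs are approximate. Moving both a little, to a difference of 1.05 and an SD of 1.45, gives 89.9% at 22 pairs, as does the normal approximation with an SD of 1.45 alone. This shows that the gap is modest. It does not close it at the values printed, by either method.

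A third is that up to 25 may be enrolled, and 25 evaluable pairs come very close to 90%. But section 9.3 attaches the 90% to 22, and the synopsis treats 22 completers as sufficient. The extra places are there to absorb fall-out. The exit rule for mixed procedures and the omission of missing data make 25 evaluable pairs a best case. Those rules bear on whether 25 can be reached; they do not alter power at 22 completers.

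Finally, the reference in section 9.2.2 to more than 95% confidence is compatible with a one-sided alpha of 0.025, which the next sentence states. It is not an error.

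**Conclusion.** The concern holds. With a true mean difference of 1.0, an SD of paired differences of 1.5 and a one-sided paired t test at 0.025, 22 pairs give 84.6% power, about 5 percentage points below the 90% stated. The shortfall is 4 pairs by the exact t calculation, or 2 by the normal approximation. At 25 evaluable pairs power is 89.2%, so the material overstatement is at the targeted minimum.

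The figure of 85% depends on 1.5 being the SD of the differences. If it is the per-knee SD, power at 22 pairs could lie above or below 90% according to a correlation that the plan does not give. On either reading section 9.3 does not support its own number. The matter should be corrected, but it does not invalidate the trial: type I error control, the endpoint and the test are unaffected.

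**What to change.** The sponsor should first confirm which SD the 1.5 is, and then amend section 9.3.

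- **If it is the SD of the paired differences:** state that 22 evaluable pairs give about 85% power and that 25 would give about 89% (paired t test, one-sided alpha 0.025, mean difference 1.0, SD of paired differences 1.5).
- **If it is the per-knee SD:** say so, state the assumed between-knee correlation, and give the power at 22 and at 25 evaluable pairs that follows from it.

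The cost is wording, plus a slightly less favourable power statement on the first reading. No patients are added. The enrolment limits, exit rule, missing-data rule, endpoint, alpha and test all stay as they are, and neither the synopsis nor section 9.2.2 needs to change.
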